### 1.2 Study Rationale

Historically, technetium Tc 99m ( $^{99m}\text{Tc}$ ) bone scintigraphy has been the standard method for first detection of bone metastases, and Taxotere® (docetaxel)-based chemotherapy was the only therapeutic option offering an overall survival (OS) advantage for patients with M1 CRPC. However, advances have recently been made in both detection and treatment of patients with M1 CRPC. Imaging technologies such as sodium fluoride F 18 ( $^{18}\text{F-NaF}$ ), positron emission tomography (PET) / computed tomography (CT), and magnetic resonance imaging (MRI) have shown improved sensitivity and specificity compared to  $^{99m}\text{Tc}$  scintigraphy and may lead to earlier detection of M1 disease than was previously possible (Even-Sapir 2006).

Novel treatments have recently been approved by the US Food and Drug Administration (FDA) for patients with M1 CRPC. They include Provenge® (sipuleucel-T) and Zytiga® (abiraterone acetate) for asymptomatic or minimally symptomatic disease; Xtandi® (enzalutamide) and Jevtana® (cabazitaxel) for treatment following docetaxel therapy; and Xofigo® (radium Ra 223 dichloride) for patients with symptomatic bone metastases.

Because there are many new therapies for M1 CRPC, including those indicated when no or minimal symptoms are present, and multiple imaging study modalities are available, clear guidance on the best timing, frequency, and imaging study modality for detecting M1 CRPC is essential.

Most clinicians use disease parameters such as serum prostate-specific antigen (PSA) levels and PSA doubling time (PSADT) to assess the risk of metastatic disease in individual patients and to make informed decisions regarding when to perform imaging studies (Kane 2003). Recently, however, Yu et al (2012) found that 32% of 2577 patients screened for a trial

enrolling patients with M0 CRPC did, in fact, have M1 CRPC at screening. These results indicate that M1 disease in patients with CRPC may be underdiagnosed.

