### **7.6.15 Imaging Studies**

Patients will undergo bone imaging studies (e.g., MRI,  $^{99m}\text{Tc}$  bone scintigraphy or  $^{18}\text{F-NaF}$  PET/CT) and soft tissue imaging studies (e.g., contrast-enhanced abdominal and pelvic CT or MRI) at the baseline visit and M0 Phase visits in order to detect any M1 disease. The imaging modality will be determined based on the study site’s standard of care and will be recorded on the eCRF.

The presence of M1 disease will be determined by the presence of bone, regional or distant nodal, or visceral metastasis, as follows:

- **Bone metastasis**

Patients with one or more unequivocal bone lesions as identified by site’s standard for imaging modality will be considered to have M1 CRPC. Patients with equivocal scans determined by standard imaging (e.g.,  $^{99m}\text{Tc}$  bone scan) will be evaluated by more sensitive imaging modalities such as CT,  $^{18}\text{F-NaF}$  PET/CT, or MRI within 1 month of the equivocal scan to confirm M1 disease status ([Adams 2011](#)).

- Regional or distant nodal metastasis

Patients diagnosed with lymph node(s) (measuring  $\geq 2$  cm on the greatest diameter) in either regional pelvic or distant lymph nodes will be considered to have M1 disease (Scher 2008).

Examples of regional lymph nodes include: hypogastric, obturator, internal and external iliac and lateral, presacral and promontory sacral lymph nodes (Adams 2011).

Examples of distant lymph nodes, which lie above the bifurcation of the common iliac arteries and outside of the confines of the true pelvis, include: aortic, common iliac, deep inguinal, superficial inguinal, supraclavicular, cervical, scalene, and retroperitoneal lymph nodes (Adams 2011).

- Visceral metastasis

Patients diagnosed with metastasis to liver, lung, brain, or other solid organ will be considered to have M1 disease.

The number and sites of bone, regional or distant nodal, or visceral metastases, if present, will be recorded on the eCRF.

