## **8.0 STATISTICAL METHODS**

### **8.1 Sample Size Considerations**

This study will identify patient characteristics at the time of the baseline imaging study that are predictive of an imaging study positive for M1 in patients with CRPC and no known M1. A minimum of 2000 patients will be registered in this study. This sample size is based on the following considerations.

The primary endpoint for the study will be the occurrence of a positive imaging study for M1 at baseline (yes or no), a binary variable. All patients with a baseline imaging study will be included in the analysis of the primary endpoint. Yu et al (2012) found that 32% of 2577 men screened for a trial enrolling patients with CRPC thought to be M0 did, in fact, have M1 CRPC, and it is anticipated that this study will have a similar finding. With 1000 patients at each of the 2 possible levels of a binary variable, for a total of 2000 patients, the variable is detectable with an odds ratio of 1.312 with 80% power using a 2-sided test at alpha = 0.05, assuming an imaging study positive for M1 at baseline in 34.95% and 29.05% of patients in level 1 and level 2 of the binary variable, respectively. However, a binary variable that is distributed at a ratio of 1:5 at baseline would allow for an odds ratio of 1.422 to be detected with 80% power assuming an imaging study positive for M1 at baseline in 38.5% and 30.6% of the patients in level 1 and level 2 of the binary variable, respectively.

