## **8.3 Analysis of Endpoints**

### **8.3.1 Primary Endpoint**

The primary endpoint for the study will be the occurrence of an imaging study at baseline that is positive for M1 (yes or no) among all patients enrolled with a baseline imaging study.

Logistic regression analyses will be used to analyze the primary endpoint. Univariate logistic regression analyses will be performed separately for each variable of interest. A multivariate logistic regression analysis will be performed including all variables of interest. A stepwise regression model selection procedure will be used to identify a model that includes explanatory factors that are independently predictive of the occurrence of a positive imaging study. The logistic regression model will be used to develop a formula for predicting the probability of a positive imaging study given specific values for the variables included in the final model.

Variables that will be considered for inclusion in the model are age, race, ethnicity, duration of disease in years from initial diagnosis to study registration, total Gleason score at diagnosis, post-RP Gleason score total, baseline ECOG performance status, baseline hemoglobin, baseline alkaline phosphatase, baseline LDH, baseline serum albumin, baseline testosterone, baseline serum PSA, baseline PSADT, first serum PSA demonstrating CRPC, baseline body mass index (BMI), prior systemic therapy (yes or no), prior ADT (yes or no), prior RP (yes or no), and prior orchiectomy (yes or no), current opioid analgesic use (yes/no), and number of prior scans. Baseline BPI scores, including worst pain in last 24 hours, least pain in last 24 hours, average pain in last 24 hours, and pain right now, will also be considered for inclusion.

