### **8.3.3 Exploratory Endpoints**

Prostate cancer treatment practice patterns will be summarized descriptively for patients with M0 CRPC and M1 CRPC. Prostate cancer interventions prior to study entry will be summarized. Additionally, the timing and sequence of prostate cancer interventions during the study will be summarized.

The identification of biomarkers in the M0 population that are predictive of an imaging study positive for M1 will be performed using logistic regression and Cox regression, as previously described. These analyses will be performed for both the primary endpoint (a positive imaging study at baseline) and the endpoint of a positive imaging study at any post-baseline time point.

The percentage of patients with CRPC with previously undiagnosed M1 at baseline will be calculated as 100 times the number of patients in the M1 analysis population divided by the total number of patients in the study.

Logistic regression analyses will be used to determine patient characteristics in the M0 population that are predictive of a positive imaging study at baseline as detected with different imaging modalities. The differing imaging modalities include MRI, 99mTc bone scintigraphy, or F-NaF PET/CT for bone imaging; and contrast-enhanced abdominal and pelvic CT or MRI for soft tissue imaging. For each imaging modality, multivariate logistic regression modeling will be used to identify factors that are independently predictive of a positive imaging study. These analyses will be performed for both the primary endpoint (a positive imaging study at baseline) and for the endpoint of a positive imaging study at any post-baseline time point.

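### Imaging modality is recorded at baseline but left out of the primary model, so the probability formula averages over an unstated modality mix and the separate per-modality fits cannot show whether predictors differ

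*Combined protocol and SAP*

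**What the plan says.** - **Collection.** Section 7.6.15 has modality follow the site's "standard of care and will be recorded on the eCRF". It gives MRI, technetium scintigraphy and NaF PET/CT as examples for bone, and CT and MRI for soft tissue. An equivocal bone scan leads to a second, more sensitive study within a month.
- **Expected differences.** Section 1.2 says the newer techniques "have shown improved sensitivity and specificity compared to" bone scintigraphy. It does not say by how much.
- **Primary model.** Section 8.3.1 begins its list with "Variables that will be considered for inclusion in the model are age, race, ethnicity" and names 22 variables plus four BPI pain scores. The nearest item to modality is the number of prior scans. Interactions are built only from listed variables that pass the univariate screen. The final model becomes a single formula for the probability of a positive study.
- **Modality analysis.** Section 8.3.3 states: "For each imaging modality, multivariate logistic regression modeling will be used to identify factors that are independently predictive of a positive imaging study". It specifies no pooled modality term, interaction test or minimum subgroup size, and it places the baseline version of this analysis in the M0 population.
- **Per-scan analysis.** Section 8.3.2 uses predictors attached to each scan but does not name modality as one.
- **Status of the list.** Section 8.3.1 allows variables to be added or dropped and defers the complete list to the SAP. The note closing the combined document says the SAP was never finalized.

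**The concern.** The endpoint is a test result, so the test used helps to determine it. If modalities detect disease at different rates, a model without modality has a mean that is wrong to some degree for each of them. This concerns the mean model, so allowing for clustering by site in the standard errors would not repair it.

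Three things are at stake, because section 1.2 says the data are meant to inform when imaging is useful:

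- A clinician who uses one modality receives a probability for a mixture.
- A predictor that is associated with modality use can pick up part of the modality effect.
- The exploratory objective on predictors by modality would rest on comparing lists from subgroups of unequal size, with no estimate of whether the effects differ.

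**Working it through.** **1. The plan's own figures (section 8.1).** The calculation takes 2000 men split evenly over a binary predictor, with positivity of 34.95% in one level and 29.05% in the other. On that basis the plan says "the variable is detectable with an odds ratio of 1.312 with 80% power using a 2-sided test at alpha = 0.05".

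Two-proportion power with pooled variance is Φ{(d√n − 1.96√[2p̄(1−p̄)]) / √[p1(1−p1)+p2(1−p2)]}, with n per level, d = 0.3495 − 0.2905 = 0.059 and p̄ = 0.32.

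- At n = 1000: (1.866 − 1.293)/0.658 = 0.870, so power is 80.8%. The odds ratio is (0.3495/0.6505)/(0.2905/0.7095) = 1.312. Both agree with the plan.
- The 1:5 case (38.5% versus 30.6%) gives 79.8% power and an odds ratio of 1.420 from the rounded rates, against 1.422 stated. Section 8.1 ties 1.422 to the unbalanced predictor, so only 1.312 is carried forward for a balanced one.

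**2. Calibration.** The 32% overall rate is section 8.1's expectation. The minority share s and the modality odds ratio are assumptions. Solve (1−s)·p + s·p′ = 0.32, where p′ has odds equal to the modality odds ratio times p/(1−p).

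- s = 20%, odds ratio 1.5: p = 30.2%, p′ = 39.3%. Check: 0.8×0.302 + 0.2×0.393 = 0.320.
- s = 20%, odds ratio 2: 28.8% and 44.7%.
- s = 50%, odds ratio 2: 24.6% and 39.4%.
- Odds ratio 1: 32% for both, no error.

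A formula without modality centres on 32% throughout. In the first case it is 1.8 points too high for the dominant modality and 7.3 points too low for the minority one.

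**3. Confounding of a null predictor (all inputs assumed).**

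- Newer-modality use 35% versus 15% across the predictor's levels, positivity 36% versus 28% by modality: 0.35×0.36 + 0.65×0.28 = 0.308, and 0.15×0.36 + 0.85×0.28 = 0.292. The odds ratio is 1.08.
- Use 50% versus 10%, positivity 40% versus 28%: 0.340 versus 0.292. The odds ratio is 1.25.

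**4. Separate fits with identical true effects.** Apply step 1's formula, with odds ratio 1.312, inside each modality:

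- 1600 men: 71.6% power
- 1000 men: 51.6%
- 400 men: 24.3%

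The chance that exactly one of two fits reaches p < 0.05 is a(1−b) + b(1−a):

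- 50/50 split: 2×0.516×0.484 = 50%.
- 80/20 split: 0.716×0.757 + 0.243×0.284 = 61%.

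These are unadjusted powers at 0.05. Section 8.3.3 sets no threshold of its own.

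**5. Events per candidate.** Pooled: 0.32×2000 = 640 positives, and 640/26 = 24.6 per candidate. In a 400-man modality: 128/26 = 4.9.

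**6. Interaction test in a pooled model.** With positivity near 32% and a balanced predictor, SE² = Σ 1/(n·0.32·0.68) over the four predictor-by-modality cells. The detectable ratio of odds ratios at 80% power is exp(2.80·SE).

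- 50/50 split: SE 0.192, ratio about 1.71.
- 80/20 split: SE 0.240, ratio about 1.96.

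**The case against.** **The list was unfinished.** Section 8.3.1 left room to add variables, so the omission need not be a decision to exclude modality. That stands as an account of how the gap arose. It does not close the gap, because no finalized SAP exists.

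**Section 8.3.3 already serves the clinician who uses one modality.** In part it does, since it seeks predictors within each modality. It gives no means of comparing them, and small modalities would have few positives per candidate.

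**No claim of difference is planned.** This is fair. The exploratory objectives ask for predictors by modality, and section 8.2.2 says no formal hypotheses are tested. The risk lies in how differing lists would be read.

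**Stronger readings.** A reader might infer that the formula fits no modality. The documents do not support that. They give no modality mix and no positivity difference, better specificity could lower positivity as well as better sensitivity raise it, and the error is small for a dominant modality. A reader might also infer that differing lists are merely an artefact of subgroup size. They can be, but a true difference is not excluded; the two cannot be separated. Serious confounding is not shown either, since the milder assumed case gives only 1.08.

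**Modality consistency.** Sections 4.0 and 7.6.15 ask for the same modality within a patient and, with an exception for moves to lower sensitivity, repeat the previous modality when M1 is found at first use of a new one. This helps follow-up comparisons but leaves differences between patients at baseline untouched.

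**Conclusion.** The point holds. A recorded variable that the protocol itself expects to affect detection is missing from the primary candidates and appears only in separate fits.

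The size of the consequence is conditional. At a 20% minority share and 32% overall, the formula is off by about 2 to 3 points for the dominant modality and 7 to 13 points for the minority one if the modality odds ratio is 1.5 to 2, and not at all if it is 1. Confounding is modest, with null-predictor odds ratios of 1.08 to 1.25 under the assumed imbalances. Discordant predictor lists would arise 50% to 61% of the time with no true difference. All of this assumes the planned 2000 men and an assumed modality split and effect. It merits correction, but it does not invalidate the primary analysis.

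**What to change.** - **Section 8.3.1.** Force baseline bone modality (scintigraphy, NaF PET/CT, MRI) and soft-tissue modality (CT, MRI) into the pooled model, exempt from screening. Code each by the initial baseline modality, so that a second scan prompted by an equivocal result does not define the term. Report the formula and its calibration by modality.
- **Section 8.3.3.** Replace or supplement the separate fits with one pooled model that has predictor-by-modality terms for the retained predictors, reported as exploratory estimates with confidence intervals. Fit the baseline version in the primary analysis population. The M0 population has no positive baseline study, so that fit cannot run as written.
- **Section 8.3.2.** Include the modality of each scan as a covariate in the per-scan analysis.
- **Metastasis-free survival.** A time-updated modality term is not recommended: scans are discretionary, so modality is seen only when one is done, and death is also an event.

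**Cost.** SAP wording and no new data. Main effects take about 3 degrees of freedom (2 for bone, 1 for soft tissue), moving expected positives per parameter from 640/26 = 24.6 to 640/29 = 22.1, counting one parameter per listed variable. Interactions add about 3 per retained predictor and will detect only large differences (ratios of odds ratios of roughly 1.7 to 2.0), which is why they should be reported as estimates with intervals.

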Although serum PSA and PSADT have been shown to convey the relative risk of developing M1 disease (Smith 2005), other biomarkers may more accurately predict a positive imaging study (Brown 2010). Interactions between blood cells and distant metastatic cells may alter the gene expression profiles of circulating cells (Ross 2012). Recent studies have shown gene expression profiling of blood cells offers a minimally invasive approach that may be prognostic for OS and the various prostate cancer disease states, including development of M1 CRPC (Olmos 2012). Therefore, as additional optional research (AOR) in this study, blood samples will be collected at baseline and each M0 Phase visit to explore changes in gene expression profiles and their correlation with development of M1 disease.

The primary purpose of this research is to describe patient characteristics predictive of an imaging study positive for M1 in the population of patients with CRPC and no known M1. These data will contribute to clinical guidance regarding the timing and utility of imaging studies in patients with CRPC.

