#### **8.2.2 Interim Analysis**

No formal interim analysis is planned for this study. Periodic summarization of the data will be performed on an ongoing basis. However, as there are no formal hypotheses being tested in this protocol, no significance-level adjustments will be made for statistical testing or estimation procedures that may be utilized.

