The above list of variables will be considered for inclusion in the final model; however, each variable will be initially screened and will be dropped from consideration for inclusion in the final model if it is shown to have little predictive value as a univariate predictor. Candidate variables for the final model will be determined by the following algorithm. A univariate logistic regression will be applied for each individual variable and all variables with  $p < 0.25$  will be considered as candidate variables for the final model. Interaction terms will also be considered for the final model. Interaction terms will be considered as candidates for the final model if the  $p$ -value for the interaction term is less than 0.25 from a model with predictor variables of variable a, variable b, and interaction of variable a and b. Only variables with  $p < 0.25$  from the univariate model screening procedure as discussed above will be considered for determining the list of interaction terms for consideration in the final model.

All candidate variables, including interaction terms identified by the algorithm discussed above, will be entered into the stepwise model selection procedure. The criteria for a variable to enter the model will be  $p < 0.05$  and variables will be retained in the model during the elimination step if  $p < 0.10$ . The final model will include all terms identified from the stepwise selection procedure and will also include all main effect terms for any interaction variables identified in the stepwise model selection procedure.

Although the above list of variables for consideration for inclusion in the model is a comprehensive one, addition or deletion of variables for consideration may occur. Therefore, the complete list of candidate variables for inclusion in the model will be provided in the final statistical analysis plan.

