**P12-1 Statistical Analysis Plan was not finalized as there was insufficient data.**

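### The imaging-risk formula is built by screening, an interaction search and stepwise selection with no internal validation, so its predicted risks are expected to be too extreme

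*Combined protocol and SAP*

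**What the plan says.** Section 8.3.1 sets out what the model is for: "The logistic regression model will be used to develop a formula for predicting the probability of a positive imaging study given specific values". It names 22 candidate variables and four Brief Pain Inventory scores, 26 in all, and builds the formula in three data-driven steps.

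1. Each variable is tested alone and kept if p<0.25.
2. Interactions are screened pair by pair, on this criterion: "interaction term is less than 0.25 from a model with predictor variables of variable a, variable b, and interaction of variable a and b". Step 1 decides which variables may form pairs: those with a low enough p-value "from the univariate model screening procedure as discussed above will be considered for determining the list of interaction terms". No other limit on pairs is stated, so the natural reading is that every pair of survivors is tried.
3. Then "All candidate variables, including interaction terms identified by the algorithm discussed above, will be entered into the stepwise model selection procedure", with entry at p<0.05 and retention at p<0.10. Main effects of any selected interaction are added back.

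Sections 8.1 to 8.7 contain no resampling, split sample, calibration check, discrimination measure or shrinkage. Section 8.2.3 mentions external datasets, but only for descriptive comparison. Section 8.3.1 leaves one item to a later document: "the complete list of candidate variables for inclusion in the model will be provided in the final statistical analysis plan". That document does not exist in final form; the SAP page reads "Statistical Analysis Plan was not finalized as there was insufficient data". Section 8.3.1 is therefore the only text that governs the formula.

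**The concern.** When the same patients choose the terms, estimate the coefficients and supply the performance figures, chance findings enter the model and look like signal. Two things follow. Performance measured on those patients is too good. The predicted risks are also spread too widely: high risks are stated too high and low risks too low. The usual measure is the calibration slope in new patients, which is 1 for a well-calibrated spread and below 1 when predictions are too extreme.

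The second consequence sits in the coefficients, so it reaches anyone who uses the formula, whether or not an AUC is reported. Section 1.2 gives the purpose: "These data will contribute to clinical guidance regarding the timing and utility of imaging studies in patients with CRPC". A formula released without any measure of how far to trust it serves that purpose poorly.

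**Working it through.** **The plan's own figure.** Section 8.1 states 80% power for one binary predictor, 1000 patients per level, 34.95% against 29.05%, two-sided alpha 0.05. The pooled two-proportion formula gives z = (0.059 - 1.96 x 0.02086)/0.02082 = 0.87, so power is 80.8%; the odds ratio is 1.312. The 1:5 case gives 79.8% to 79.9%, with an odds ratio of 1.420 from the rounded rates (stated: 1.422). Both reproduce. They concern detection of one predictor, not development of a prediction model.

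**Size of the search.** Expected positives: 0.32 x 2000 = 640.
- Main effects only: 640/26 = 24.6 positives per candidate.
- Pairs: 26 x 25/2 = 325 if all variables pass the first screen; 13 x 12/2 = 78 if half pass; about 141 if two thirds pass.
- With all pairs open: 640/(26 + 325) = 1.8 positives per candidate term. About 0.25 x 325 = 81 null interactions would pass the second screen by chance.

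**Simulation of the section 8.3.1 algorithm.** From the protocol: N=2000, 32% positive, 26 candidates, all p-value thresholds. Assumed, because the documents give no values: effect sizes, correlations, and no true interactions unless stated. Each fitted formula was tested on 20,000 new patients. Set A has eight true main effects (log-odds per SD 0.40, 0.35, 0.30, 0.25, 0.20, 0.20, 0.15, 0.15), with 60 replicates, or 40 in the two rows with correlation 0.2. Set B has three to six true main effects, correlation 0.15 in general and 0.5 to 0.7 within blocks, eight binary predictors and 100 replicates.

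| Setting | False interactions in model | AUC apparent / new | Slope, as planned | Slope, same selection without interactions |
|---|---|---|---|---|
| A, uncorrelated | 3.0 | 0.703 / 0.679 | 0.86 | 0.95 |
| A, blocks, 7 binary | 3.9 | 0.687 / 0.654 | 0.80 | 0.92 |
| A, correlation 0.2, mixed signs | 2.8 | 0.689 / 0.659 | 0.82 | 0.91 |
| A, correlation 0.2, same sign | 14.1 | 0.787 / 0.734 | 0.73 | 0.97 |
| A halved, uncorrelated | 2.6 | 0.623 / 0.577 | 0.61 | 0.75 |
| A halved, blocks | 2.9 | 0.612 / 0.565 | 0.57 | 0.74 |
| B, moderate | 13.0 | 0.747 / 0.684 | 0.68 | 0.96 |
| B, weak | 5.7 | 0.625 / 0.573 | 0.57 | 0.91 |

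The number of false terms follows the number of eligible pairs. In the same-sign row all 26 variables pass the first screen and 325 pairs are open; in the mixed-sign row 74 are. With no signal at all (Set B), the AUC is 0.541 apparent against 0.499 new, and the slope is about 0.

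**True interactions (Set A, uncorrelated and block settings).** With two or three real ones, slopes stay at 0.81 to 0.83, and at 0.68 with halved main effects and two real interactions. The search then gains 0.003 to 0.017 in new-patient AUC over main effects only. With none real, it loses 0.007 to 0.009 in the 60-replicate runs with full effects.

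**Unselected 26-variable model.** AUC optimism is 0.017 to 0.026 and the slope 0.85 to 0.91.

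**Smaller N (Set B, moderate).** N=1000: optimism 0.098, slope 0.54. N=500: 0.148 and 0.39. N=250: 0.178 and 0.31.

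**What a slope means for a patient.** With predictions centred on 32%, true logit = -0.754 + slope x (stated logit + 0.754).
- Slope 0.8: a stated 60% is -0.754 + 0.8 x 1.159 = 0.17, or 54%; a stated 10% is -0.754 - 0.8 x 1.443 = -1.91, or 13%.
- Slope 0.6: the same stated risks correspond to about 49% and 17%.

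**Whether resampling recovers the truth.**
- Set B, moderate, 8 datasets x 12 whole-procedure bootstraps: AUC 0.754 apparent, 0.677 corrected, 0.684 in new patients; slope 0.64 estimated against 0.65.
- Set A, four settings, 24 datasets each: the apparent AUC was too high by 0.026 to 0.036. The bootstrap was too low by 0.016 to 0.028. Repeated 10-fold cross-validation was within 0.006. Slope errors were -0.07 to -0.12 for the bootstrap and -0.03 to -0.07 for cross-validation, from the rounded means.

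**The case against.** Four objections deserve an answer.

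*The study is descriptive.* Section 8.2.2 says "as there are no formal hypotheses being tested in this protocol, no significance-level adjustments will be made for statistical testing or estimation procedures". A reader might infer that the complaint is uncontrolled type I error. The documents do not support that reading, because no confirmatory claim is made. The statement does not answer the point here either: overfitting of a formula is separate from significance levels.

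*No AUC is promised.* This is correct. A reader might infer that an inflated AUC will be published, or that the formula itself becomes guidance. The plan names no performance measure, and section 1.2 says that the data will contribute to guidance. The point therefore concerns the formula's predicted risks, and performance only if it is measured on the same patients.

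*Screening and stepwise selection are ordinary practice at this sample size.* Largely fair. Without interactions the same rules give slopes of 0.91 to 0.97, falling to about 0.75 only in the halved-effect settings. It would be wrong to blame all three steps equally. It would also be wrong to treat the full 26-variable model as immune: it is overfitted too, generally less, although in the uncorrelated Set A setting it is close (slope 0.87 against 0.86).

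*Some interactions may be real.* Then the search improves discrimination, so the figures do not show that interactions should be dropped. The slope stays below 1 all the same.

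**Conclusion.** The concern holds. Followed as written, section 8.3.1 is expected to yield a formula with risks that are too extreme, and no planned step would reveal it. The direction was the same in every setting tried.

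The size depends on assumed effects and correlations, so no single figure should be quoted. At N=2000 and 32% positive, with some real signal, the AUC is overstated by about 0.02 to 0.06 and the new-patient slope is about 0.57 to 0.86. The interaction search is the main driver. That rests on reading the screen as covering all pairs of survivors, which is natural but not explicit.

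The SAP page cites insufficient data, so the 2000 patients may not have been reached. The documents give no achieved number and do not show that the formula was ever fitted, so a reader should not infer that an overfitted formula was released. Nothing here makes the power calculation in section 8.1 wrong.

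**What to change.** Add one or two sentences to section 8.3.1:

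- The whole selection procedure (univariate screen, interaction screen, stepwise selection, added main effects) is repeated within resamples of the primary analysis population, by bootstrap or repeated 10-fold cross-validation.
- The optimism-corrected AUC and calibration slope are reported with the formula.
- If the corrected slope is clearly below 1, the published coefficients are shrunk by it and the intercept is re-estimated.

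Either resampling method will do. Cross-validation was closer in the Set A check and the bootstrap was nearly unbiased in the small Set B check, which does not settle a preference. Resampling only the final model, with its terms fixed, would miss most of the problem.

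The cost is computing time and a less favourable reported performance, with the AUC lower by roughly 0.02 to 0.06 under the assumptions above. No new data are needed. Limiting the formula to interactions named in advance is a trade-off for the sponsor and is not part of this fix.
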